5.3 Procedures for participants identified as HIV infected

This study may identify persons who become infected with HIV 1 (expected to be very rare) during follow-up of enrolled HIV negative participants. Study staff will provide participants with their HIV test results in the context of post-test counseling. A blood sample will be obtained for HIV drug resistance testing conducted through the standard national GEMS protocol for drug resistance surveillance. These results will be communicated to participants as soon as they are available. Persons identified as HIV infected during the study will be initiated on free HIV treatment and will also be referred to nearby HIV care services for follow up at completion of this trial. For participants who are pregnant and become infected

with HIV during study follow-up, every effort will be made to facilitate immediate access to programs for preventing mother-to-child HIV transmission for appropriate antiretroviral treatment to reduce the probability of HIV transmission from mother to child.

5.4 Procedures for follow up and care for pregnant cisgender women after DOT PrEP

Pregnant cisgender women will be followed closely for any adverse events and pregnant outcomes. Routine health services including counseling for prevention of maternal to child HIV transmission will be provided at Thika clinic during the study period or referred to health facility of their choice.

At each scheduled pharmacological visit, antenatal records will be reviewed, and assessment of fetal heart tones will be conducted. After 8 weeks of DOT PrEP, pregnant cisgender women will be linked to continue PrEP at the clinic of their choice, including at the Thika site clinic itself, permitting seamless access to PrEP for and continuation for HIV prevention after the study. After 8 weeks of DOT PrEP, if a pregnant cisgender woman chooses not to continue with PrEP for protection against HIV, they may have two additional visits after their last PrEP dose – one visit at week 9 and a second visit within weeks 10 to 16. In the event of pregnancy loss during study follow up, study drug procedures and follow up will be terminated and women will be linked to appropriate clinical standard care including continued access for PrEP. After completing DOT phase of study, pregnant women will have observation visits until end of the study or up to the infant's first birthday (12 months) after delivery whichever occurs first to obtain pregnancy outcomes (i.e., term live birth, preterm birth, birth defects or pregnancy loss) and infant growth outcomes (i.e., weight, head circumference and height). Post DOT maternal/infant visit will 1 (i.e., birth visit), 6, and 12 months. Medical and medication history at birth will be reviewed and will consist of information recorded on medical records at birth as well as information obtained at the Birth Visit (Month 1 post-delivery).

The following should be source documented as part of medical and medications history at the Birth Visit: **Pregnancy/birth outcomes:** Term live birth, preterm birth, birth defects or pregnancy loss, Sex at birth Birth length, weight, and head circumference at birth (obtain from medical records; these measurements will also be performed by study staff at the infant Birth Visit), Apgar scores at one and five minutes (obtained from medical records)

Infant growth outcomes: obtained at 1, 6 and 12 months will include: Length, weight, and head circumference.

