2.6 Enrollment Targets

A cohort of up to 72 cisgender women who meet the inclusion and exclusion criteria described in Section 3 below will be enrolled at the KEMRI Thika Research Site, in Thika, Kenya. The target enrollment is to have at least 60 evaluable participants (both pregnant and non-pregnant) at the end of the study (i.e. have complete set of all protocol pharmacological samples). As described in Section 3.8, women with incomplete set of pharmacological samples will be replaced but no more 20% or up to 72 total cisgender women who agree to enroll. i.e., 54 low risk non-pregnant cisgender women and 18 pregnant cisgender

women at elevated risk of HIV. The cohort of 54 cisgender women who accept PrEP will be randomized 1:1:1: **2, 4, or 7** DOT doses per week to help differentiate poor and modest from perfect dosing. Pregnant cisgender women will receive only daily DOT dosing.

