3.8 Replacement of Study Participants

Data from people who permanently discontinue study treatment will be used in analyses. Study participants who miss two consecutive scheduled dosing or miss any pharmacological samples or permanently discontinue DOT PrEP will be replaced so that approximately 60 evaluable participants complete the study. No more than 20% of the target population (n=60) will be replaced for maximum of 72 participants. Data from subjects who discontinue prematurely will be used in analyses. In the non-pregnant cohort, cisgender women who get pregnant will be replaced but continue to be followed up to the end of their scheduled protocol study follow up. Seroconversions (unlikely though possible) will not be replaced.

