5.2 Enrollment and Follow up Procedures

Up to 72 evaluable HIV uninfected participants (54 non pregnant and 18 pregnant cisgender women) will be enrolled and followed up for 16 weeks: 8 weeks with DOT PrEP, and up to 8 weeks for post drug kinetics sampling – one visit in week 9 and an additional visit within weeks 10 to 16 (i.e. 2 visits in total). Enrollment must occur within 30-day screening window. An eligible participant who is unable to schedule a study entry visit within the 30-day screening window must be re-screened prior to entry into the study. All enrolments will be scheduled on specific days to avoid confusion in implementing the proposed dosing and sampling scheme. Study entry visit (enrollment) through week 8 visit will include an adverse effect questionnaire along with medical and medication review. Safety labs and vitals can be ordered as needed at any visit.

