- Urine pregnancy test
- Medical, sexual, contraception, antenatal and vaccine history review
- AE assessment
- Concomitant Medication Review
- DOT
- Finger stick for DBS

Clinic visit 7: Week 5 (Dose 35) visit:

- Study bloodwork: WB, DBS, PBMC, plasma
- Study urine
- Medical, sexual, contraception, antenatal and vaccine history review

- AE assessment
- Concomitant Medication Review
- DOT

Clinic visit 8: Week 6 (Dose 42) visit:

- Study bloodwork: WB, DBS, PBMC, plasma
- Medical, sexual, contraception, antenatal and vaccine history review
- AE assessment
- Concomitant Medication Review
- DOT
- Study urine

Clinic visit 9: Week 7 (Dose 49) visit:

- Study bloodwork: WB, DBS, PBMC, plasma
- Study urine
- Medical, sexual, contraception, antenatal and vaccine history review
- AE assessment
- Concomitant Medication Review
- DOT

Clinic visit 10: Week 8 (Dose 56) visit:

- HIV rapid test
- Urine β HCG
- Study bloodwork: WB, DBS, PBMC, plasma
- Finger stick for DBS
- Study urine
- Vaginal biopsy: **Non-pregnant cohort only**
- Vaginal swab
- Hair collection
- Safety Labs: Creatinine
- Medical, sexual, contraception, antenatal and vaccine history review
- AE assessment
- Concomitant Medication Review
- DOT

Post DOT PrEP visits (Week 9): One visit (Clinic visit #11) within week 9, at least 48 hours after the last DOT PrEP dose.

- Study bloodwork: plasma, WB, DBS, PBMC
- Study urine

Post DOT PrEP visits (Week 10-16): One visit (Clinic visit #12) at least 7 days after week 9 visit (i.e., the visit can occur any time between 2-8 weeks after the last DOT F/TAF PrEP which is about week 10 and week 16 since enrollment)

- Study bloodwork: plasma, WB, DBS, PBMC
- Study urine
- Hair collection

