5.2.3.1 Specimen collection

All pharmacological samples must be collected as per protocol-specified schedule. Each protocol-specified pharmacological sampling visit will have a window of up to 3 days (up to week for hair) for sample collection. The following pharmacological samples will be collected as follows:

Blood collection

A blood sample will be obtained at protocol specified visits to process plasma, whole blood, DBS, and PBMCs. On a given study day blood collection, up to 21-mL draw with no planned timing relationship with dosing. The blood will be collected from an arm vein by trained clinic staff according to study site policies and procedures.

The schedule of protocol visits and procedures are outlined in Table 5.

Table 5: Schedule of protocol visit schedule and procedures.

	Screening	Entry	DOT PrEP Period (weeks)										Post DOT Period	
Timeline (weeks)			W1		W2	W3	W4	W5	W6	W7	W8	W9	W10-16	
			Day 4	Day 7										
Clinic Visits #		1	2	3	4	5	6	7	8	9	10	11	12	
Procedure														
Informed consent	x													
Medical, sexual, contraception, antenatal history review, vaccine history	x	x	x	x	x	x	x	x	x	x	x			
Physical and obstetric exam ^a	x													
Fetal ultrasound for pregnant women*	x													
Dispense back up PrEP medication ^e		x												
Issue medical calendar		x												
AE assessment		x	x	x	x	x	x	x	x	x	x			
Safety Labs ^{a,c}	x	[x]									x			
Urine β HCG ^a	x	[x]					x				x			
HBS Ag	x													
HIV-1 rapid test ^a	x	[x]					x				x			
Hair collection							x				x		x	
hDNA		x		x										
Study Bloodwork ^d (WB, plasma, DBS, PBMC)**		x	x	x	x	x	x	x	x	x	x	x	x	
Vaginal tissue- non-pregnant only ^f			x	x			x				x			
Vaginal swab		x	x	x			x				x			
DBS by fingerstick			x	x			x				x			
Study Urine ^d		x	x	x	x	x	x	x	x	x	x	x	x	
Concomitant Medication Review	x	x	x	x	x	x	x	x	x	x	x			
STI testing		x												
DOT ^b		x	x	x	x	x	x	x	x	x	x			

[x] Indicated if screening occurred more 30 days before planned enrollment. The screen and entry visits must be ≤ 30 days apart.

*If women has no record of fetal ultrasound for the current pregnancy, ultrasound must be conducted before enrollment.

**Blood works for pregnancy women only at week 0, 1, 2, 4, 6, 8, 9

a. Safety labs or vitals can be performed as needed at any time

b. DOT performed if applicable per randomization schedule

- c. Protocol-specified safety labs include: CBC, HBAg, Creatinine clearance, in addition to monthly HIV testing and urine pregnancy tests.

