9 LABORATORY SPECIMENS AND BIOHAZARD CONTAINMENT

9.1 Laboratory evaluations and specimen collections

The following safety and monitoring laboratories will be collected at regular intervals during the study as described above: complete hematology panels, pregnancy tests (urine), and HIV (rapid or regular), serum creatinine, (estimated creatinine clearance), and HBV surface Ag test. The HIV and HBV tests will be used to screen HIV-negative volunteers for inclusion in the study. The tests are provided according to established laboratory procedures at site. These clinical laboratories/sites conform to CAP and/or CLIA-regulations, and the results will be posted to the medical record as positive or negative.

All pharmacological samples will be collected, processed, and stored according to standard operating procedures developed by the Colorado Antiviral Pharmacology Laboratory. On each pharmacological sample visit day, samples will be collected without regard to the dosing time within each day (i.e., sampling at convenience times rather than troughs). The only exception will be at the entry visit to be obtained at pre-dose. We will take a comprehensive approach to establish benchmark adherence-concentration thresholds for cisgender women and pregnant cisgender women using daily DOT TDF/FTC

PrEP by collecting samples for pharmacological measurements in multiple biologic matrices: plasma, whole blood, DBS, PBMCs, and vaginal tissue (non-pregnant cisgender women only) and archiving urine and hair samples. All cisgender women (non-pregnant and pregnant) will contribute to this comprehensive assessment during the up to 16 weeks of follow up (8 weeks of DOT PrEP and up to 8 weeks post DOT PrEP for post drug kinetics). Within each group, we will collect pharmacologic samples (plasma, whole blood, DBS, PBMCs) to measure the respective concentrations of TDF/FTC moieties at day 4 and weekly up to 8 weeks with daily DOT PrEP dosing and at week 9 and weeks 10-16 post DOT PrEP period, and in nonpregnant cisgender women, vaginal tissue at day 4, week 1, 2, 4, and 8.

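### Pregnant women have three incompatible post-DOT sampling schedules, and the week-9 timing rule does not separate off-drug from on-drug samples

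*Combined protocol and SAP*

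**What the plan says.** The default after week 8 is stated in 5.4: "After 8 weeks of DOT PrEP, pregnant cisgender women will be linked to continue PrEP at the clinic of their choice". Section 2.5.2 says the same, and eligibility for this cohort requires elevated HIV risk and willingness to use PrEP.

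Post-DOT sampling of pregnant women is then described in three ways:

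- **Section 5.4:** "if a pregnant cisgender woman chooses not to continue with PrEP for protection against HIV, they may have two additional visits", one at week 9 and one within weeks 10 to 16, counted from her last PrEP dose.
- **Table 5 footnote (5.2.3.1):** "Blood works for pregnancy women only at week 0, 1, 2, 4, 6, 8, 9". Week 9 carries no condition about stopping PrEP, and weeks 10-16 are absent. The footnote covers blood only. Table 5 still marks urine and hair at weeks 10-16, with no exemption for pregnancy.
- **Sections 5.2 and 9.1:** 5.2 gives both cohorts "one visit in week 9 and an additional visit within weeks 10 to 16 (i.e. 2 visits in total"), for post-drug kinetics. Section 9.1 adds: "All cisgender women (non-pregnant and pregnant) will contribute to this comprehensive assessment during the up to 16 weeks of follow up".

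Section 5.2.2 times visit 11 as "at least 48 hours after the last DOT PrEP dose". In Table 5 both observed dosing and concomitant-medication review end at visit 10.

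On completeness, 2.6 describes evaluable participants as those who "have complete set of all protocol pharmacological samples". Section 3.8 says that participants who "miss any pharmacological samples or permanently discontinue DOT PrEP will be replaced", up to a maximum of 72 enrolled.

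**The concern.** A site cannot follow all three descriptions, and the conflict falls on the path that most of this cohort is expected to take. Two things are at stake.

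The first is what the post-DOT samples mean. A woman who moves to clinic-supplied daily PrEP satisfies a 48-hour rule counted from her last DOT dose while still taking drug. Nothing scheduled at visits 11 or 12 would show this. If her sample were used for the post-drug kinetics named in 5.2 and 9.1, it would be treated as washout when it is not.

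The second is the count of evaluable women. Neither 2.6 nor 3.8 says which sample set applies to a pregnant woman who continues PrEP. Depending on the answer, she is complete, or she is missing samples and has to be replaced from a capped enrolment.

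**Working it through.** **Inputs.** Half-life of TFV-DP in DBS about 17 days (5.2.1, 7.3.1); DOT period 8 weeks = 56 days; target 60 evaluable, replacements at most 20%, maximum 72 (2.6, 3.8); 54 non-pregnant and 18 pregnant women.

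**The plan's own count.** 60 × 1.20 = 72, and 54 + 18 = 72. The cap reproduces.

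**Week-9 level, off drug and on drug.** First-order kinetics with k = ln 2 / 17 = 0.0408 per day.

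- Week 8 as a fraction of steady state: 1 − exp(−56k) = 0.898, matching the approximately 90% in 7.3.1.
- Off drug for 7 days: exp(−7k) = 0.752, so about 75% of the week-8 level.
- Daily dosing continued in full for 7 days (assumption): (1 − exp(−63k)) / (1 − exp(−56k)) = 0.923 / 0.898 = 1.028, so about 103% of week 8.
- Off drug at other times: 92% at 2 days, 57% at 14 days, 10% at 56 days. The last two span the visit-12 window of 2 to 8 weeks.

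Partial adherence after week 8 would fall between 75% and 103%. The plan records nothing that would place a woman on that range.

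**Evaluable count under each reading.** Let c be the number of pregnant women who continue PrEP and are counted as missing a post-DOT sample.

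| Required set for a woman who continues PrEP | c | Evaluable pregnant | Maximum evaluable in total |
|---|---|---|---|
| 5.4: post-DOT visits not scheduled for her, so not missed | 0 | 18 | 72 |
| Table 5 blood list, week 9 given | 0 | 18 | 72 |
| 5.2/9.1 in full, or Table 5 urine and hair at weeks 10-16, with visits not offered under 5.4 | 0 to 18 | 18 − c | 72 − c |

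In the last row, 72 − c < 60 once c > 12. If all 18 continue, the maximum is 54. This supposes that all 54 non-pregnant women are evaluable. If only 45 were, the total would be at most 63 − c and would fall short once c > 3.

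**A related conflict.** Section 9.1 asks for blood at day 4 and weekly to week 8 in each group. The footnote omits weeks 3, 5 and 7 for pregnant women. Taken literally as the required set, 9.1 would make every pregnant woman sampled by the footnote incomplete, whatever she does after week 8.

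**The case against.** The best reply is that 9.1 is general text, and that the Table 5 footnote and 5.4 are the cohort-specific provisions a site would actually use. The mismatch at weeks 3, 5 and 7 supports this. On that view a woman who gives week-9 blood has complete blood, and a visit that 5.4 does not schedule is not missed. Section 5.4 also counts from the last PrEP dose of any kind, so its own visits are washout visits.

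Much of that stands, and it rules out several stronger readings that a reader might infer:

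- **That 5.4 bars women who continue PrEP from the visits.** It does not offer them; it contains no express prohibition.
- **That 3.8 makes every such woman non-evaluable.** Section 3.8 is a replacement rule and 2.6 holds the definition. The result follows only under the last row of the table. Someone who gave week-9 blood does not lack it.
- **That the analysis would keep mainly women who abandon PrEP.** Section 3.8 retains data from those who discontinue and does not drop a replaced woman's data. No analysis in 7.3 is restricted to evaluable women.
- **That the half-life in pregnancy will be biased.** The kinetic model in 7.3.1 uses day 4 to week 8 only, and no washout model is specified. Bias arises only if post-DOT samples from women still on drug are used for the stated kinetic purpose.
- **That 15 of 18 must stop PrEP to meet the sample size.** The 15 in 7.4 concerns precision of the steady-state mean, which women who continue still supply at week 8.

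What the reply does not answer: the footnote's week-9 draw has no condition on drug status, visit 11 is timed from the DOT dose, and Table 5 keeps urine and hair at weeks 10-16. Section 5.2.3.1 lists both among the pharmacological samples that must be collected on schedule.

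**Conclusion.** The inconsistency is real and should be resolved before sites count replacements or post-DOT samples are analysed. Its reach is limited to the interpretation of post-DOT samples in the pregnant cohort and the evaluable and replacement counts. The week-8 benchmark and the dose-proportionality model are unaffected.

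For the samples, the gap is about 75% against about 103% of the week-8 DBS level at seven days. It rests on a 17-day half-life, taken to apply in pregnancy, and on full daily dosing among those who continue. For the counts, the effect runs from no loss to a shortfall below 60 when more than 12 of 18 continue, according to which passage sets the required samples. The larger loss is a worst case, not a prediction; the documents give no expected continuation rate.

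**What to change.** 1. Reconcile Table 5, 5.2, 5.4 and 9.1 into one sampling schedule for the pregnant cohort. Cover blood, urine and hair after week 8, and the weeks 3, 5 and 7 blood conflict. This concerns sampling only and leaves each woman's decision about PrEP untouched.
2. In 2.6 and 3.8, define the required set for pregnant women by the reconciled DOT-period samples to week 8. Require post-DOT samples only of women who are off drug.
3. At visits 11 and 12, record the date of the last TDF/FTC dose from any source. Use a sample for post-drug kinetics only if the woman has stopped drug and that visit's own timing condition is met counting from that date: 48 hours for visit 11, and its separate window for visit 12.

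The cost is protocol wording, one extra date field (self-reported where dosing was not observed), and fewer pregnant women contributing washout data.

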6 SAFETY MONITORING AND ADVERSE EVENT REPORTING

6.1 Safety Monitoring

Close cooperation between the Protocol Chair, study site Investigator(s), DAIDS Medical Officer, protocol Biostatistician, and other study team members will be necessary in order to monitor participant safety and to respond to occurrences of toxicity in a timely manner.

The study site Investigators are responsible for continuous close monitoring and management of AEs in conjunction with IoRs. The study site is required to have detailed SOPs describing methods for AE reporting and toxicity management to ensure that AEs are reported and managed in accordance with the protocol and for alerting the Protocol Safety Review Team (PSRT) if unexpected concerns arise. The team will have regularly scheduled conference calls during the period of study implementation, and additional ad hoc calls will be convened if required.

A sub-group of the Protocol Team, including the Protocol Chair and co-Chair, DAIDS Medical Officer, site clinicians, and the Seattle-based Study safety monitor will serve as members of the PSRT. The PSRT provides support to site clinicians regarding individual participant clinical management (e.g., questions related to eligibility, toxicity management, clinical holds of study drug, permanent discontinuations, etc.).

The Seattle-based Study safety monitor will review all safety data. The Seattle-based Study safety monitor will prepare routine study conduct and safety reports for the PSRT, which will meet by conference call approximately every 6 months or as needed.

6.2 Clinical Data Review

A multi-tiered safety review process will be followed for the duration of this study. The study site investigators are responsible for the initial evaluation and reporting of safety information at the participant level, and for alerting the PSRT if unexpected concerns arise.

Participant safety data will also be monitored by the Seattle-based Study safety monitor, who review incoming safety data for completeness and consistency on an ongoing basis. Events identified as questionable, inconsistent, or unexplained will be queried for verification. AE reports submitted in an expedited manner to the DAIDS Safety Office will be forwarded to the DAIDS Medical Officer for review.

The Seattle-based Study safety monitor will prepare routine study conduct and safety reports for the PSRT which will meet by conference call approximately every 6 months and will review accrual and retention data, as well as safety data. More frequent or *ad hoc* reviews of safety data may be conducted by the PSRT as needed. A recommendation to stop the trial may be made by the PSRT at any such time that the team agrees an unacceptable type and/or frequency of AEs has been observed. If at any time a decision is made to discontinue the study product in all participants, DAIDS will notify appropriate regulatory agencies, as well as the site IoRs, who will notify the responsible IRBs expeditiously.

6.3 Adverse Event Definition and Reporting

An AE is defined as any untoward medical occurrence in a clinical research participant administered an investigational product and which does not necessarily have a causal relationship with the study product (TDF/FTC). As such, an AE can be an unfavorable or unintended sign (including an abnormal laboratory finding, for example), symptom or disease temporally associated with the use of an investigational product, whether or not considered related to the product.

Study participants will be provided a 24-hour telephone number and contact information and instructed to contact the study clinician to report any AEs they may experience. For life-threatening events, they will also be instructed to seek immediate emergency care. Where feasible and medically appropriate, participants will be encouraged to seek evaluation where the study clinician is based, and to request that the clinician be contacted upon their arrival. With appropriate permission of the participant, whenever possible, records from all non-study medical providers related to AEs will be obtained and required data elements will be recorded on study CRFs. All participants reporting an AE will be followed clinically, until the AE resolves (returns to baseline) or stabilizes.

Study site staff will document in source documents and the appropriate e-CRF AEs (Grade 1 and higher clinical AEs, as well as Grade 2 and higher laboratory AEs, and any AE (clinical or laboratory) that leads to a study product hold (temporary or permanent) will be captured on AE e-CRFs) reported by or observed in enrolled (defined as after randomization has occurred) study participants regardless of severity and presumed relationship to study product. AE severity will be graded per the DAIDS Table for Grading Adult and Pediatric Adverse Events, Version 2.1 corrected, July 2017.

